5.1. Summary of Study Design

Study ITRN is a Phase 3, prospective, randomized, double-blind, outpatient, multinational, multicenter, 2-group, parallel, active-controlled study conducted in patients with type 2 diabetes mellitus (T2D) currently treated with basal insulin in combination with at least 1 prandial insulin injection OR premixed insulin with at least 2 injections daily. The study includes a 1-week screening period and an 8-week lead-in period, followed by a 26-week treatment period, and a 4-week safety follow-up period. [Figure 5.1](#) illustrates the study design.

All patients who complete the 4-week safety follow-up visit (Visit 801) and have treatment-emergent anti-insulin lispro antibodies response that have not returned to the pre-specified baseline range (Visit 2) will be asked to participate in follow-up to monitor insulin lispro antibody levels for up to 26 weeks after Visit 801. The follow-up consists of Visit 802 and Visit 803.

[figure not shown]
5.2. Determination of Sample Size

Assuming a noninferiority margin (NIM) of 0.4%, no true difference between treatment arms, and a standard deviation (SD) of 1.1%, 568 completers (284 in each treatment group) will provide at least 99% power to show noninferiority between LY900014 and insulin lispro in change from baseline to 26 weeks in hemoglobin A1c (HbA1c) using the upper limit of a 2-sided 95% confidence interval (CI) (LY900014 – insulin lispro). **CCI**

5.3. Method of Assignment to Treatment

Patients who meet all criteria for enrollment will be randomized to double-blind treatment at Visit 8. Assignment to treatment groups will be determined by a computer-generated random sequence using an interactive web-response system (IWRS). Patients will be randomized to 1 of the 2 treatment groups in 1:1 ratio (double-blind LY900014 administered at meal time, double-blind insulin lispro administered at meal time). Stratification will be by country, HbA1c stratum ($\leq 8.0\%$, $> 8.0\%$ at Visit 7), and type of basal insulin during the lead-in period (glargine U-100 or degludec [U-100 or U-200]), and number of prandial doses at study entry (< 3 , ≥ 3).

Abbreviations: T = telephone visit; wk = week.

- a At Visit 2, patients treated with insulin aspart, insulin glulisine, regular insulin, or premixed insulin will be transferred to insulin lispro. At Visit 2, patients treated with a basal insulin regimen other than insulin glargine U-100 or insulin degludec will be transferred to an allowed study basal regimen of insulin glargine U-100 once or twice daily or insulin degludec U-100 or U-200 once daily. At Visit 8, patients will be randomized to either insulin lispro or LY900014 and continue their basal insulin regimen.
- b Titrate basal insulin.
- c Titrate prandial insulin (insulin lispro or LY900014).
- d Patients will discontinue study insulins at Week 26.
- e Eligible patients will have visits at approximately 3-month intervals for up to 26 weeks after Visit 801 for follow-up of insulin lispro antibody levels.

Figure 5.1. Illustration of study design.

6. A Priori Statistical Methods

6.1. General Considerations

Statistical analysis of this study will be the responsibility of Eli Lilly and Company (hereafter Lilly). Any change to the data analysis methods described in the protocol will require an amendment ONLY if it changes a principal feature of the protocol. Any other change to the data analysis methods described in the protocol, and the justification for making the change, will be described in this SAP and/or in the clinical study report (CSR). Additional exploratory analyses will be conducted, as deemed appropriate.

Statistical analyses for Japan are described in [Appendix 2](#). Statistical Analyses for the Maximum Extended Enrollment (MEE) Addendum are described in [Appendix 3](#).

For purposes of analysis, the following populations are defined in [Table 6.1](#):

Table 6.1. Patient Populations

Population	Description
Entered	All patients who give informed consent.
Enrolled	All patients who receive at least 1 dose of open-label insulin lispro in the 8-week lead-in period.
Randomized	All patients who are randomly assigned to study treatment at Visit 8. Treatment group will be defined on the basis of the treatment the patients are assigned.
Safety	All randomized patients who receive at least 1 dose of the randomly assigned investigational product (IP). Treatment group will be defined on the basis of the treatment the patients are assigned.
Completer	Patients included in the randomized population who have completed Week 26 of study treatment without permanent discontinuation of IP. Treatment group will be defined on the basis of the treatment the patients are assigned.
Per Protocol	Patients included in the randomized population who have completed Week 26 of study treatment without permanent discontinuation of IP and without significant protocol deviations through Week 26 that would significantly impact the primary objective. Treatment group will be defined on the basis of the treatment the patients actually receive.

Unless otherwise stated, the efficacy analyses will be conducted on the Randomized Population, and the safety analyses will be conducted on the Safety Population.

The primary analysis is for the treatment period through Week 26.

Unless otherwise noted, all tests of treatment effects will be conducted at a 2-sided alpha level of 0.05, and CIs will be calculated at 95%, 2-sided. All tests of interactions between treatment groups and other factors will be conducted at a 2-sided alpha level of 0.10.

The definitions of baseline and post-baseline for the efficacy and safety analyses depend on which analysis period is being used. The following analysis periods will be used:

- Lead-in Period – Visits 2 to 8
- 26-Week Treatment Period – from randomization to Week 26 prior to discontinuation of IP and from randomization to Week 26 (including all data regardless of IP use)
- 26-Week Treatment Period and Safety Follow-Up Visit – from randomization to Visit 801 (including all data regardless of IP use)

The data on IP is defined based on the following rules:

- For data only measured at an office visit
 - MMTT postbaseline data will be classified as on IP if the MMTT performance date is prior to or on the last IP dose date
 - Other postbaseline data (for example, vital signs, safety laboratory tests, and questionnaires) will be considered as on IP if the measurement was performed at or prior to the cutoff date defined as 14 days after the last IP dose date
- For data collected as running records with an exact date stamp such as adverse events (AEs) and diary entries where the dates of the measures were not tied with the date of an office visit, postbaseline data with dates \leq (last study drug dose date +1) will be considered as data on IP.

Table 6.2 describes the rules for determining the patient population, baseline and postbaseline observations for the different analysis periods.

For continuous measures, summary statistics will include sample size, mean, SD, median, minimum, and maximum for both the actual and the change from baseline measurements. Least-squares (LS) means and standard errors derived from the analysis models will also be displayed. Treatment comparisons will be displayed showing the treatment difference LS means and the 95% CIs for the treatment differences, along with the p-values for the treatment comparisons.

For categorical measures, summary statistics will include sample size, frequency, and percentages. Fisher's exact test or Pearson's chi-square test will be used for treatment comparisons.

For laboratory values, both conventional (CN) and Systeme International (SI) units will be presented. Therefore, both % and mmol/mol will be presented for HbA1c and both mg/dL and mmol/L will be presented for glucose measurements.

All baseline measures will be analyzed using an analysis of variance (ANOVA) model that has treatment as the model term.

Table 6.2. Baseline and Post-Baseline Definitions and Patient Population by Study Period and Type of Analysis

Study Period/Analysis	Patient Population	Baseline Observations	Post-Baseline Observations
Lead-In Period			
TEAEs	All Enrolled Patients	Prior to first dose of open-label insulin lispro (or Visit 2 date if the dose date is missing)	The entire lead-in period after first dose of open-label insulin lispro and prior to the first dose of IP (or Visit 8 date if the dose date is missing).
Basal, prandial, and total insulin doses, and prandial/total insulin dose ratios continuous analysis	All Randomized Patients	Visit 2	Visits 3 to 8 prior to initiation of IP
Weight MMRM and ANCOVA	All Randomized Patients	Last of Visits 1-2	Visits 3–8 AND Last of Visits 3-8
26-Week Treatment Period (including Safety Follow-Up Visit where applicable)			
HbA1c MMRM and ANCOVA (efficacy estimand)	All Randomized Patients with a baseline and at least 1 post-baseline observation while on IP	Last of Visits 7-8	Visits 11, 13, 15, and 18 prior to discontinuation of IP AND Last of Visits 9-18 prior to discontinuation of IP
HbA1c ANCOVA (ITT estimand)	All Randomized Patients with a baseline and at least 1 post-baseline observation	Last of Visits 7-8	Visit 18 with imputation for patients who discontinue study prior to Visit 18
HbA1c categorical analyses longitudinal logistic regression and LOCF logistic regression	All Randomized Patients with a baseline and at least one post-baseline observation while on IP	Last of Visits 7-8	Visits 11, 13, 15, and 18 prior to discontinuation of IP AND Last of Visits 9-18 prior to discontinuation of IP
1-hr and 2-hr PPG and other MMTT variables (efficacy estimand)	All Randomized Patients with a post-baseline observation while on IP	Visit 8 prior to initiation of IP	Visit 18 prior to discontinuation of IP
1-hr and 2-hr PPG and other MMTT variables (ITT estimand)	All Randomized Patients with a post-baseline observation	Visit 8 prior to initiation of IP	Visit 18 regardless of IP use
10-point SMBG, basal, prandial insulin doses, prandial/total insulin dose ratios	All Randomized Patients with a baseline and at least one post-baseline observation	Visit 8 prior to initiation of IP	Visits 11, 13, 15, and 18 prior to discontinuation of IP AND Last of Visits 9-18 prior to discontinuation of IP

Baseline and Post-Baseline Definitions and Patient Population by Study Period and Type of Analysis

Study Period/Analysis	Patient Population	Baseline Observations	Post-Baseline Observations
1,5-AG	All Randomized Patients with a baseline and at least one post-baseline observation	Visit 8 prior to initiation of IP	Visits 11, 15, and 18 prior to discontinuation of IP AND Last of Visits 9-18 prior to discontinuation of IP
Health outcomes: ITSQ, EQ-5D-5L, EQ-VAS, WPAI-GH	All Randomized Patients with a baseline and a post-baseline observation	Last of Visits 1-8	Last of Visits 9-18 prior to discontinuation of IP
Safety Laboratory Tests (chemistry, hematology, lipids) – continuous analysis	All Patients in the Safety Population with a baseline and a post-baseline observation	Last of Visit 1-8	Visit 18 (planned) AND last of Visits 9-18 (planned including early discontinuation visits) regardless of IP use
Safety Laboratory Tests (chemistry, hematology, lipids) – categorical analysis	All Patients in the Safety Population with a normal baseline (with respect to the direction being analyzed) and a post-baseline observation	Visits 1-8 (including unplanned tests)	Visits 9-18 (including unplanned tests) regardless of IP use
TEAEs	All Patients in the Safety Population	Prior to first dose of randomized IP (or Visit 8 date if the dose date is missing) but after the first dose of open-label insulin lispro in the Lead-in Period	From first dose of randomized IP to last dose of randomized IP AND From first dose of randomized IP to Visit 801
Hypoglycemia events	Safety Population	All Visits 2-8	All Visits 9-18 prior to discontinuation of IP
Weight and vital signs	All Patients in the Safety Population with a baseline and a post-baseline observation	Last of Visits 2-8	Visits 9-18 prior to discontinuation of IP AND Visits 9-801 regardless of IP use
Anti-insulin lispro antibodies	Safety Population	Visit 2	Visits 3-801 regardless of IP use

Abbreviations: 1,5-AG = 1,5-Anhydroglucitol; ANCOVA = analysis of covariance; EQ-5D-5L = European Quality of Life - 5 Dimensions 5 Level; EQ-VAS = EuroQol visual analogue scale; HbA1c = hemoglobin A1c; IP = investigational product; ITSQ = Insulin Treatment Satisfaction Questionnaire; ITT = intention-to-treat; LOCF – last-observation-carried forward; MMTT = mixed meal tolerance test; MMRM = mixed-effect model repeated measures; PPG = postprandial glucose; SMBG = self-monitored blood glucose; TEAE = treatment-emergent adverse event; WPAI-GH = Work Productivity and Activity Impairment General Health.

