7.2. Method of Treatment Assignment

Patients who meet all criteria for enrollment will be randomized to double-blind treatment at Visit 8. Assignment to treatment groups will be determined by a computer-generated random sequence using an interactive web-response system (IWRS). Patients will be randomized to 1 of the 2 treatment groups in 1:1 ratio (double-blind LY900014 administered at meal time, double-blind insulin lispro administered at meal time). Stratification will be by country, HbA1c stratum ($\leq 8.0\%$, $>8.0\%$ at Visit 7), and type of basal insulin during the lead-in period (glargine U-100 or degludec [U-100 or U-200]), and number of prandial doses at study entry (<3 , ≥ 3).

The IWRS will be used to assign all IP during the study, including insulin lispro during the lead-in period. The IWRS will be used to assign prefilled pens containing double-blind IP to each patient randomized to the 2 blinded study groups. Site personnel will confirm that they have located the correct prefilled pens by entering a confirmation number found on the prefilled pen into the IWRS.

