10.2. Populations for Analyses

For purposes of analysis, the following populations are defined:

Population	Description
Entered	All patients who sign informed consent.
Enrolled	All patients who receive at least 1 dose of open-label insulin lispro in the 8-week lead-in period.
Randomized	All patients who are randomly assigned to study treatment at Visit 8. Treatment group will be defined on the basis of the treatment the patients are assigned.
Safety	All randomized patients who receive at least 1 dose of the randomly assigned IP.
Completer	Patients included in the randomized population who have completed Week 26 of study treatment without permanent discontinuation of IP.
Per Protocol	Patients included in the randomized population who have completed Week 26 of study treatment without permanent discontinuation of IP and without significant protocol deviations through Week 26 that would significantly impact the primary objective. Treatment group will be defined on the basis of the treatment the patients actually receive.

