Eligibility	Inclusion/Exclusion	Previous insulin therapy	Mixed (monitoring and clinical database)	CRF Prior Diabetes Therapies / Concomitant Therapy panel data to indicate not compliant with entry criteria #3, #32, #33. CCI [REDACTED]
Investigational Product	Treatment Assignment/ Randomization Error		Mixed (monitoring and clinical database)	IWRS data entry errors that impact patient stratification, for example, lab data indicated different strata from IWRS stratification report. Dispensing error: Patient is assigned to a treatment, but site gave a different treatment to the patient.
Investigational Product	Unblinding		Non Programmable (monitoring)	Any inadvertent unblinding affecting patients, investigator or sponsor.
Investigational Product	Patient Took Medication Not Fit for Use		Non Programmable (monitoring)	Study Drug not fit for use administered to patient.
Investigational Product	Other	Use of expired CT material	Non Programmable (monitoring)	CCI [REDACTED]

Description of Important Protocol Deviations

Category	Sub-categories	Description	Source	Methods of Identification
Study Procedures	Violation of Discontinuation Criteria		Mixed (monitoring and clinical database)	Patients not discontinued from treatment and/or study despite having met protocol specified discontinuation criteria. CCI [REDACTED] Protocol Section 8.
Study Procedures	Excluded Conmeds		Mixed (monitoring and clinical database)	CRF Prior Diabetes Therapies / Concomitant Therapy panel data to indicate not compliant with entry criteria #34 and study-specific restriction on concomitant therapies Table ITRN.8 in the study protocol. CCI [REDACTED]
Study Procedures	Lab/Imaging Criteria	Missing HbA1c at baseline/at the primary endpoint	Mixed (monitoring and clinical database)	Central laboratory data to indicate that a). HbA1c is not collected at both Visit 7 and Visit 8 or b). HbA1c is not collected at the primary endpoint (only applicable to patients who completed the primary endpoint without early discontinuation from the study).
Study Procedures	Visit Schedule Criteria		Programmable (clinical database)	CRF Subject Visit panel data to indicate that 2 consecutive office visits are completely missing.
Study Procedures	Other	Electronic Clinical Outcomes Assessment (eCOA)	Programmable (clinical database)	Comparison of patient data from CRF and eCOA to identify randomized patients who have no ed diary data entered.

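### Safety is grouped by assigned insulin, its entry wording can be read to leave out patients given only the wrong blinded pens, and no safety analysis by insulin received is planned

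*SAP*

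**What the plan says.** SAP Section 6.1, Table 6.1, sets two rules for the Safety population. The entry rule is "All randomized patients who receive at least 1 dose of the randomly assigned investigational product (IP"). The grouping rule is "Treatment group will be defined on the basis of the treatment the patients are assigned". Protocol Section 10.2 has the same entry rule, "All randomized patients who receive at least 1 dose of the randomly assigned IP", but its Safety row gives no grouping rule, so the SAP supplied it.

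Unless otherwise stated, "the safety analyses will be conducted on the Safety Population" (SAP Section 6.1). In Table 6.2 the treatment-period rows for adverse events, hypoglycemia, safety laboratory tests, vital signs and antibodies all use that population. The on-treatment adverse event window there is "From first dose of randomized IP to last dose of randomized IP".

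SAP Table 6.3 lists this among the important protocol deviations: "Dispensing error: Patient is assigned to a treatment, but site gave a different treatment to the patient". The one population that follows exposure is Per Protocol, where "Treatment group will be defined on the basis of the treatment the patients actually receive". Its stated use is a sensitivity run of the HbA1c MMRM (SAP Section 6.11.3).

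**The concern.** The plan foresees that some patients may be handed the other arm's insulin but does not say how their safety data are then handled. Two cases follow from Table 6.1.

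- **Only the other arm's pens taken.** Read literally, the patient has had no dose of the assigned product and is outside the Safety population, although exposed to blinded study insulin.
- **Both insulins taken.** The patient is in the population, and every event is counted under the assigned arm, including events that arose on the other insulin.

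The distinction matters most for harms tied to the formulation. Both products are insulin lispro 100 U/mL (protocol Section 5.5). LY900014 differs by treprostinil, citrate and other excipients (protocol Section 3.2). Injection site and hypersensitivity comparisons therefore ask what those excipients do to the people who received them. Counting by assignment mixes the arms and usually pulls a true difference toward none, which is the less cautious direction for a harm.

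**Working it through.** The plan gives no figure on this point. Its only power statement concerns HbA1c and plays no part here. The check is therefore textual, with an illustration of size on assumed rates.

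**Step 1. Follow each patient type through the text.**

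| Blinded insulin taken | In Safety (Table 6.1)? | Counted under | Adverse event window (Table 6.2) |
|---|---|---|---|
| Assigned only | Yes | Assigned, which is also received | Clear |
| Both | Yes | Assigned, for all events | Unclear which doses open and close it |
| Other arm's only | No on a literal reading; yes if the phrase means the blinded product | Assigned, if included | No start date on a literal reading |

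No other readable section of the SAP adds a safety analysis by insulin received.

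**Step 2. How many patients.** Inputs: 670 randomized 1:1 (protocol Sections 5.2 and 7.2), so 670 / 2 = 335 per arm. Assumed error rate: 0.5% to 1%. Then 0.005 × 670 = 3.4 and 0.01 × 670 = 6.7, or about 3 to 7 patients over both arms.

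**Step 3. Expected bias.** Suppose m patients in each arm take the other insulin throughout and are counted as assigned. With f = m / 335 and true event proportions p1 (LY900014) and p0 (lispro), the arms show

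- LY900014: (1 − f) p1 + f p0
- lispro: (1 − f) p0 + f p1

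For m = 3, f = 3 / 335 = 0.90%. With assumed p1 = 3.0% and p0 = 0.5%, the arms show 2.978% and 0.522%, a risk ratio of 5.70 against a true 6.0. All event rates here are assumptions.

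| m per arm | f | Apparent ratio, true 6.0 (3.0% vs 0.5%) | Apparent ratio, true 2.0 (10% vs 5%) |
|---|---|---|---|
| 1 | 0.30% | 5.90 | 1.99 |
| 3 | 0.90% | 5.70 | 1.97 |
| 7 | 2.09% | 5.34 | 1.94 |
| 17 | 5.07% | 4.58 | 1.86 |

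The range from Step 2 is 3.4 / 2 = 1.7 to 6.7 / 2 = 3.4 patients per arm, so it lies near the second row or above.

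**Step 4. Misplaced events.** If 7 patients in all were misplaced and each had a 3% chance of the event, the expected number of misplaced events is 7 × 0.03 = 0.21. A single misplaced patient with an event moves an arm's incidence by 1 / 335 = 0.30 percentage points. At an assumed 0.5% incidence an arm expects 335 × 0.005 = 1.7 events, so such a move would be visible for a very rare event, though it is unlikely to happen.

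**The case against.** The strongest reply is that the entry wording need not exclude anyone. Lead-in lispro is also investigational product, assigned through the IWRS (protocol Section 7.2), and the SAP speaks of randomized product to set the blinded insulin apart from it (Table 6.2 and Section 6.12.3). On that reading, a patient given the wrong blinded pens stays in. This stands as far as it goes: the wording is ambiguous, and exclusion is one reading of it. It leaves the grouping rule as it is.

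Second, the errors should be rare. The protocol has a safeguard: "Site personnel will confirm that they have located the correct prefilled pens by entering a confirmation number found on the prefilled pen into the IWRS". Blinded product is dispensed at Visits 8, 11, 13, 15, 16 and 17 (protocol Section 2), so wholly wrong exposure needs repeated errors, or one error followed by early stopping. This also stands. Mixed exposure is the more realistic case, and misattribution the more realistic problem.

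Third, grouping by assignment keeps the randomized comparison, is pre-specified, and does not contradict a protocol that is silent on safety grouping. That is right, and the assigned view is defensible. The gap is that it is the only view planned.

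Fourth, important deviations are summarized by arm for all randomized patients (SAP Section 6.9), so the errors will be reported. This helps only in part: Table 6.3 puts dispensing errors in the same subcategory as IWRS entry errors affecting strata, and a count does not link a patient's events to the insulin taken.

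A reader might infer that these patients' harms would be lost. The documents do not support that. All serious adverse events are listed (SAP Section 6.12.2), deaths are listed for all enrolled patients (6.12.3), severe hypoglycemia reported after randomization is listed (6.12.4.1), and narratives cover all patients in the study with deaths, serious events, discontinuations due to adverse events, or pregnancy (6.12.8). What is at stake is their place in the comparative tables.

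**Conclusion.** The point holds as a minor one. The plan foresees wrong-treatment dispensing, groups safety by assignment, uses an entry phrase open to two readings, and plans no safety view by insulin received. Affected patients' events would be counted under an insulin they did not take or, on the literal reading, left out of the comparative tables.

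The size is probably very small. On the assumed 0.5% to 1% error rate, about 3 to 7 of 670 patients are affected, and an assumed risk ratio of 6.0 would appear as roughly 5.7 to 5.9. Neither the error rate nor the event rates come from the documents. The calculation also assumes wrong exposure throughout, which overstates the bias for patients who took both insulins.

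It is tempting to conclude that one misplaced patient could change the safety findings. The documents give no expected counts for severe hypoglycemia or hypersensitivity, so that cannot be shown. The efficacy analyses of all randomized patients, the sample size and the power are unaffected.

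**What to change.** 1. In SAP Table 6.1, define Safety as all randomized patients with at least one dose of any double-blind product. Make the same change to protocol Section 10.2, and record it with its justification as SAP Section 6.1 requires for changes of method.
2. In Table 6.2, run the adverse event window from the first to the last dose of double-blind product.
3. Analyse safety by insulin actually received, using the insulin taken for most of the exposure when both were taken. At minimum, keep the assigned grouping and pre-specify the as-received grouping as a sensitivity analysis of adverse events, hypersensitivity, injection site reactions and severe hypoglycemia, triggered if any mismatch occurs.
4. List every patient whose received and assigned insulin differ, with event dates.

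The text changes are short. The work lies in identifying mismatches: IWRS records alone may not be enough, because a pen handed out in error need not appear there, and Table 6.3 gives monitoring together with the clinical database as the source. The rule should be fixed before unblinding, so that no one chooses afterwards where a serious event belongs.

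There are two downsides. The as-received grouping departs from randomization for a few patients, and a majority rule cannot correctly place every event of a patient who took both insulins. The listing in item 4 is there for those events.
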